6.4. Rules for study discontinuation

Criteria for premature discontinuation of the study

- Withdrawal of consent,
- Protocol violation,
- Intolerance to treatment,
- Voluntary discontinuation of treatment,
- Intake of a forbidden treatment during the study,
- Proved pregnancy,
- Decision at the discretion of the investigator.

Criteria for stop the study

The study will be considered terminated at the end of the participation of the last patient entered into the study, and when all collected data needed for evaluation have been verified and validated.

7. Data Management and statistics

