2.1. Primary objective and primary endpoint

The main objective is to demonstrate the efficacy of 2L[®]ALERG versus placebo on the symptoms of allergic rhinitis and allergic rhino-conjunctivitis in patients with seasonal allergy to grass pollen.

The primary endpoint will be the area under the curve (AUC) of the overall score established according to the total 5 symptoms score (T5SS) and medication score (MS) according to time from the start of treatment until the end of the patient follow-up.

The five symptoms (sneezing, rhinorrhoea, nasal pruritus, eye itching and tearing, and nasal obstruction) will be assessed daily by patients on a scale from 0 (no symptoms) to 3 (severe symptoms) giving a total score ranging from 0 to 15.

The rescue medications (RM) allowed in the first-line adjuvant treatment will be codified to establish a score.

The allowed RM are the oral antihistamines (two points per day of use) or local treatment (nasal or eye; a point per day), and the ocular cromoglycate (one point per day).

In case of failure or in case of insufficiency of rescue medications mentioned above, the nasal topical corticosteroids (one point per day of use) will be allowed.

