5.5. Monitoring of compliance

The drugs will be sent to investigators (GPs in private practice). The treatment beginning two months before the expected grass pollen peak, the investigator will deliver it to the patient for 3 months (3 boxes) at V0, then for three other months at V1.

The investigator will ask the patient to bring back drug boxes (full and empty blisters) at each visit.

The counting of the remaining capsules will be made by the investigator. In case the patient would come in consultation a few days before the end of the treatment period, the patient will be allowed to keep the blister to complete the sequence.

A global compliance will be calculated for each patient on the total duration of treatment. Global compliance will be acceptable if it is between 80% and 120%. If values <80% or> 120%, the patient will be eliminated from the analysis according to the protocol and will be taken into account in the analysis by intention to treat.

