6.1. Study procedures

The following demographic data will be collected during the first visit: date of birth, gender, ethnic group, weight, height, smoking habits and alcohol use status.

Medical history, treatment history, concomitant treatments and patient's physical examination will also be documented during V0.

The allergy must be confirmed by positive skin test and/or the presence of IgE for grasses (prick test defined as positive if higher than or equal to half the negative control; IgE are positive if at least class 3 (\geq 3.5 kU/L); these tests must have been made at the latest during the first visit.

A patient diary will be given to each patient.

- For evaluation of the total 5 symptoms score T5SS and rescue medication RS, it is essential that patients note **every day** the symptoms (sneezing, rhinorrhoea, nasal pruritus, itching and/or eye tearing and nasal obstruction) intensity, and the rescue medications, in their patient diary.
- It is also essential that the patient takes note **every day** of his/her QoL by filling in three questions included in his/her diary card: Did you sleep well? Can you work normally? How do you feel?
- It is also imperative that patients note the date of the start of treatment and the date of onset of symptoms.

This patient diary will be given to the patient at each visit, and will be brought back at the next visit, it will be reviewed and validated by the investigator and will be part of the CRF (Case Report Form).

All relevant (related to allergy) concomitant medications (except rescue medications) taken by the patient during the study period will be recorded at each visit in the CRF.

The AEs and SAEs will be recorded at V1 and V2 in order to assess safety.

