A Statistical Analysis Plan (SAP) will be written by the Biostatistician of the CRO in charge of the study. This document will constitute the reference document as far as statistical analyses and statistical methodologies are concerned. It will be approved and signed by the Sponsor and the Principal Investigator before the last patient last visit at the latest.

Study cohorts

Two cohorts will be defined:

- Intention-to-treat (ITT) cohort including all patients having been exposed to at least one dose of the investigational product and in whom at least one efficacy or safety information has been collected after V0.
- Per protocol (PP) cohort including of the ITT having strictly adhered to the protocol and having a compliance between 80% and 120%.

The primary cohort for the statistical analyses will be the ITT cohort.

The patients who will prematurely stop the study will not be replaced.

Statistical methods

The IBM SPSS Statistics (Version 21.0 and eventual upgrades) software will be used throughout statistical analyses.

Missing values will not be replaced, nor extrapolated.

Classical descriptive statistics will be used to describe the patient population at baseline.

The two groups will be compared at baseline using independent Student's t tests for continuous variables and Mann-Whitney's tests, Chi-square tests or Fisher's exact tests for discrete variables.

The superiority of the active treatment over placebo will be demonstrated using an independent Student's test comparing the over-time T5SS (corrected with RM) evolution (AUCs) of the two study groups over the whole treatment period. A P value lower than 5% will be considered statistically significant.

The comparisons between the two study groups in terms of secondary endpoints will be done using the appropriate statistical methods, as they will be described in the SAP. No correction being applied for the multiplicity of endpoints, p values lower than 5% will be considered with caution, as indicative only of potential statistically significant differences between the two groups for the secondary endpoints.

8. Pharmacovigilance and management of adverse events

8.1.Definitions

Adverse events

An adverse event is defined as any untoward medical occurrence in a patient or a participant in a clinical trial, whether or not considered drug related.

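### Section 6.4 makes stopping the capsules or taking a forbidden drug a ground for leaving the study, and nothing secures later diary days for the ITT comparison of AUCs

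*Protocol*

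**What the plan says.** Section 6.4 of the protocol heads a bare list "Criteria for premature discontinuation of the study". Beside withdrawal of consent it contains "Voluntary discontinuation of treatment", "Intake of a forbidden treatment during the study", intolerance and protocol violation. It draws no line between ending the capsules and ending participation.

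The outcome data come from a paper diary, handed out at V0 and V1, which "will be brought back at the next visit" (section 6.1). The flow chart in section 6.2 has no early-exit visit. The follow-up in section 8.5, two months beyond the end of the study, concerns adverse events only.

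The primary endpoint is an AUC of the combined symptom and medication score "according to time from the start of treatment until the end of the patient follow-up" (section 2.1). In section 7.2, "The primary cohort for the statistical analyses will be the ITT cohort" and "Missing values will not be replaced, nor extrapolated". Section 7.2 also says that patients who stop early are not replaced. Under section 5.5, a patient with compliance outside 80 to 120% leaves the per-protocol analysis but "will be taken into account in the analysis by intention to treat".

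**The concern.** An AUC accumulates over days, so a patient whose diary stops early has either a low AUC or none. If the written rule is followed, the analysis is labelled ITT but moves towards a comparison of completers, or of partial sums with full sums.

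The loss need not be random. The forbidden drugs in section 5.3 are oral or injectable corticosteroids and anti-leukotrienes. Patients plausibly reach for these when permitted rescue medication fails, so the rule could remove the most symptomatic days. Intolerance and voluntary stopping may also differ by arm.

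This is a matter for the protocol. A SAP can choose how to score an incomplete diary, but it cannot recover days that were never collected.

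**Working it through.** **1. The plan's own figures (section 7.2).** For a difference of 25 (80 against 55), two-sided alpha of 0.05 and a two-sample t-test, the noncentral t gives power of 90.7% with 32 per arm at SD 30 and 90.6% with 43 per arm at SD 35. Enrolment is 40/(1 − 0.20) = 50 per arm. These figures reproduce and are not in question. At the planned 40 evaluable per arm, power is 95.7% (SD 30) or 88.4% (SD 35).

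**2. Severity-related stopping.** All of the following is assumed: 50 per arm, normal AUCs with means 80 and 55, 20% stopping overall, and one stopping rule for both arms with correlation 0.5 to the full AUC. Stopping is then 25.7% placebo and 14.3% active at SD 30, and 24.9% and 15.1% at SD 35.

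Under the fix, if active stoppers lose a share L of the benefit over the whole AUC, the difference is 25 − 25 × L × (active stopping rate):
- SD 30: 25 − 25 × 0.5 × 0.143 = 23.2 and 25 − 25 × 1 × 0.143 = 21.4
- SD 35: 25 − 25 × 0.5 × 0.151 = 23.1 and 25 − 25 × 1 × 0.151 = 21.2

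Powers come from 20,000 simulated trials; repeat runs differ by up to about a point.

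| Handling of stoppers | Difference, power at SD 30 | Difference, power at SD 35 |
|---|---|---|
| Omitted | 22.4, 93% | 22.4, about 85% |
| Truncated AUC, 25–75% kept | about 18, 88–89% | about 18.5, 82% |
| Fix, L = 0.5 | 23.2, 96% | 23.1, 89% |
| Fix, L = 1 | 21.4, 90–91% | 21.2, 81% |

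Omission falls inside the range that the fix itself would deliver. Only truncated scoring falls clearly below it.

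**3. No true effect, unequal stopping unrelated to severity.** Both means are 80 and stoppers keep on average a share s of their AUC. The expected difference (placebo minus active) is 80 × (1 − s) × (active rate − placebo rate).
- 10% placebo, 30% active: 80 × 0.75 × 0.20 = 12 for s = 0.25; 80 × 0.50 × 0.20 = 8 for s = 0.50; 80 × 0.25 × 0.20 = 4 for s = 0.75, all favouring active. With s spread over 25–75%, SD 30 and 50 per arm, two-sided type I error is about 23%, nearly all in favour of active.
- 15% and 25%: 80 × 0.50 × 0.10 = 4, with type I error about 10%.
- 20% and 20%: 0, with type I error nominal.
- 30% placebo, 10% active: −8, against active.

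**4. True difference of 25, 20% stopping in each arm, related to severity within the arm.** Without the fix, power is 97% (omitted) or 98% (truncated) at SD 30, and 92% or 94% at SD 35. With the fix the difference is 25 − 25 × 0.5 × 0.20 = 22.5 down to 25 − 25 × 1 × 0.20 = 20.0. Power is then 95% down to 86% at SD 30 and 87% down to 75% at SD 35.

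**The case against.** The protocol nowhere says that the diary ends. Someone who stops early already holds the diary issued at V0, which is meant to run to V1, three months later and about one month past the expected peak. Section 5.5 keeps poor compliers in the ITT analysis, which would fit a reading in which stoppers continue to be followed. This stands as far as it goes: the end of the diary is inferred. But a patient out of the study has no scheduled visit at which to return a diary, and section 5.5 secures no later data.

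The larger distortions depend on a scoring rule (partial AUCs summed as they stand) that the protocol does not state and the SAP may avoid. They also depend on assumed stopping rates. Assigning the whole 20% drop-out to these rules is generous, since it also covers consent withdrawal and loss to follow-up. Permitted rescue medication makes severity-driven exit less likely. All of this stands and limits what can be said about size.

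The fix can also lower power, and under equal stopping it does so in the cases shown. It creates a new problem too: forbidden drugs suppress symptoms but earn no points in section 2.1. Both objections stand, and the second must be dealt with in the fix.

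**Conclusion.** The point holds on grounds of validity. Section 6.4 as written turns several treatment events into study exits, while the primary analysis needs diary days to the end of follow-up from everyone in the ITT cohort. Any bias can go either way, and its size is unknown because stopping rates by arm, their timing and the scoring of incomplete diaries are not given.

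A reader might infer three stronger things that the documents do not support:
- That the protocol orders the diary to stop. It is silent.
- That type I error is inflated. It is nominal under equal stopping. The figure of about 23% needs both an assumed 10%/30% split and truncated sums.
- That continued diaries would restore the planned difference of 25 and raise power. That would require active stoppers to keep the full benefit. Under severity-related stopping, the fix (21 to 23; about 90 to 96% at SD 30) and simple omission (about 22; 93%) are close.

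The change is worth making because it is cheap and removes a loss that no later analysis can repair.

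**What to change.** In section 6.4, separate the end of study treatment from the end of the study:
- Only withdrawal of consent or loss to follow-up ends data collection.
- All other stoppers keep the existing daily diary, record any forbidden drug in it and attend V1 and V2. All their diary days enter the ITT AUC.
- Before unblinding, fix a medication score for days on oral or injectable corticosteroids or anti-leukotrienes. It could be set, for example, no lower than the highest rescue score in section 2.1, which is two points per day for oral antihistamines.

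The rules on who stops treatment, and the care they then receive, do not change.

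The cost is a wording change in the protocol and patient information, one scoring rule, and continued diaries for at most about 20 patients (20% of 100). That number is a ceiling, because no wording recovers patients who withdraw consent or are lost. The price may also include some power, since off-treatment days dilute the difference.

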7.1. Data collection and handling of study data

Data collection

Data collection will be done on paper CRF for each patient,

The patient will fill in the patient diary card given by the investigator and bring it back at the next visit. The investigator will check the patient diary card and will keep it in the patient CRF The sponsor will be responsible for the printing of CRFs (NCR carbon paper) and patient diaries, which will be sent to each investigator.

The persons allowed to fill in the CRF are identified in the delegation of responsibilities sheet witch is to be kept in the Trial Master File.

Data coding

By signing this protocol the investigator and all the staff are committed to keep confidential the identities of the patients participating in the study.

Each patient will be identified by a numerical code consisting of 4 digits: YY/ZZ (YY corresponding to the centre number and ZZ to the patient number).

A form will be made available to the investigator so he could note the correspondence between the numeric code and the patient's identity. He/she must keep this document in his/her Trial Master File.

Collection Data Processing

The compilation of clinical data will be based on the structuration of a clinical database (IBM SPSS Data Entry Builder) and the creation of input screens in the image of CRF and diary card in accordance with the Protocol and the legislation currently in force.

This database will be validated and documented appropriately.

All data will undergo a double data entry process in the database, by two independent encoders, using the IBM SPSS Data Entry Interviewer software.

Based on the regular cleaning of data, queries will be generated to the investigational centres. The answers to these queries will also be encoded in the database.

7.2.Biostatistics

Sample size calculation and justification

The objective of the study will be to show the superiority of 2L[®]ALERG over placebo in the treatment of patients suffering from seasonal allergy to grass pollen.

For the sample size calculations two references have been used. The first is a study conducted with 2[®]LALERG versus placebo in patients with a pollen allergy. ^[1]

The second is a more theoretical publication from Clark and Schall (2007) supporting the recommendations made in a World Allergy Organization document on methodological aspects of immunotherapy trials. The average of the Average Rhinoconjunctivitis Total Symptom Score (ARTSS) and Average Rescue Medication Score (ARMS) should be considered as a primary efficacy variable in clinical trials of immunotherapy for allergic rhinoconjunctivitis. ^[35]

Version 1.0, 04 February 2016, Page 25

The global score calculated in the paper of [name] et al. (2011)^[1], taking into account the T5SS total score and the RMS total score, fits very well with the recommendation from Clark and Schall (2007)^[35].

The Figure 5 of [name] et al.'s paper has been used to evaluate the area under the curve (AUC) of global score for the placebo and 2L[®]ALERG groups. ^[1]

[figure not shown]

Fig. 5. Comptages polliniques et évolution du score global (moyenne et écart-type) dans les groupes actif et placebo pendant la période d'étude.

The values were approximately 80 for the placebo group and 55 for the treated group (a reduction of about 30% with the active treatment. These values have been used to build several sample size scenarios.

Scenario	1	2	3	4	5
Test significance level, α	0.050	0.050	0.050	0.050	0.050
1 or 2 sided test?	2	2	2	2	2
Group Placebo mean, μ1	80.000	80.000	80.000	80.000	80.000
Group 2L [®] ALERG mean, μ ₂	55.000	55.000	55.000	55.000	55.000
Difference in means, μ1 - μ2	25.000	25.000	25.000	25.000	25.000
Common standard deviation, σ	20.000	25.000	30.000	35.000	40.000
Effect size, $\delta = \mu_1 - \mu_2 / \sigma$	1.250	1.000	0.833	0.714	0.625
Power(%)	90	90	90	90	90
n per group	15	23	32	43	55
Total N completed patients	30	46	64	86	110

A sample size of 32 patients in each group will have 90% power to detect a difference in means of 25 (the difference between a placebo group mean, μ_1 , of 80 and a 2L[®]ALERG group mean, μ_2 , of 55) assuming that the common standard deviation is 30 using a two group t-test with a 0.05 two-sided significance level.

With a sample size of 43 patients in each group, the same assumptions are valid with a common standard deviation of 35.

The final recommendation will be to include 50 patients per group in order to achieve at least 40 evaluable patients per group taking into account a potential drop-out rate of 20%.

Statistical analyses

A Statistical Analysis Plan (SAP) will be written by the Biostatistician of the CRO in charge of the study. This document will constitute the reference document as far as statistical analyses and statistical methodologies are concerned. It will be approved and signed by the Sponsor and the Principal Investigator before the last patient last visit at the latest.

Study cohorts

Two cohorts will be defined:

- Intention-to-treat (ITT) cohort including all patients having been exposed to at least one dose of the investigational product and in whom at least one efficacy or safety information has been collected after V0.
- Per protocol (PP) cohort including of the ITT having strictly adhered to the protocol and having a compliance between 80% and 120%.

The primary cohort for the statistical analyses will be the ITT cohort.

The patients who will prematurely stop the study will not be replaced.

Statistical methods

The IBM SPSS Statistics (Version 21.0 and eventual upgrades) software will be used throughout statistical analyses.

Missing values will not be replaced, nor extrapolated.

Classical descriptive statistics will be used to describe the patient population at baseline.

The two groups will be compared at baseline using independent Student's t tests for continuous variables and Mann-Whitney's tests, Chi-square tests or Fisher's exact tests for discrete variables.

The superiority of the active treatment over placebo will be demonstrated using an independent Student's test comparing the over-time T5SS (corrected with RM) evolution (AUCs) of the two study groups over the whole treatment period. A P value lower than 5% will be considered statistically significant.

The comparisons between the two study groups in terms of secondary endpoints will be done using the appropriate statistical methods, as they will be described in the SAP. No correction being applied for the multiplicity of endpoints, p values lower than 5% will be considered with caution, as indicative only of potential statistically significant differences between the two groups for the secondary endpoints.

8. Pharmacovigilance and management of adverse events

8.1.Definitions

Adverse events

An adverse event is defined as any untoward medical occurrence in a patient or a participant in a clinical trial, whether or not considered drug related.

All adverse events encountered during the study, which are observed by the physician or patientreported, will be recorded in the CRF in the section provided for this purpose.

The intensity of adverse events will be quoted as follows:

- 1 = mild
- 2 = moderate
- 3 = severe

For each adverse event, the investigator will have to rule on the causal relationship to the medical product on the following scale: none, possible, probable or certain.

Adverse events or serious adverse events (AEs or SAE)

An AE is considered as SAE when it:

- Results in death,
- Involves life-threatening,
- Results in incapacity or temporary or permanent disability,
- Requires or prolongs patient hospitalization,
- Causes congenital anomaly or neonatal
- Is medically significant (requires care to avoid worsening)

Serious Adverse Reaction (SAR)

A SAR is a SAE considered related to the investigational study product.

Expected adverse reaction or events

An expected adverse event is an event mentioned in the most recent version of the Summary of Product Characteristics (SmPC) for drugs already having a marketing authorization.

The expected effects or serious adverse events will be subject to a delayed declaration by the sponsor to the competent authorities.

Unexpected Serious Adverse Reactions (SUSARs)

Unexpected Serious Adverse Reactions (SUSARs) are events where the nature, severity, frequency or developments are not consistent with product information, with practiced acts and with methods used during the study, as defined in the SmPC.

Unexpected serious adverse events will be subject to a statement within 7 days after their knowledge by the sponsor to the competent authorities.

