2.2. Secondary objectives and secondary endpoints

The secondary objectives will be to compare the effect of 2L®ALERG versus placebo on:

- Symptoms of allergy (not corrected by the use of rescue medication),
- Use of rescue medication,
- Evolution of the quality of life (QoL) using 3 daily specific questions included in the patient's diary card: Did you sleep well? Can you work normally? How do you feel?
- Safety (AEs and SAEs).

The secondary endpoints will be:

- Total 5 symptoms score (T5SS) and individual scores of 5 symptoms
- Consumption of rescue medications
- Evaluation of the QoL: AUC (total score of 3 questions of QoL included in the diary card on the Y-axis, and time on X axis) during the entire follow-up period
- Frequency, severity and causality relationship of AEs and SAEs.

[figure not shown]
3. Study design

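### The protocol's ban on replacing or extrapolating missing values does not fit a cumulative AUC: it leaves a leaver's primary outcome undefined, and each available reading can bias the confirmatory t-test

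*Protocol*

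**What the plan says.** - **Missing data (7.2, Statistical methods).** "Missing values will not be replaced, nor extrapolated". No exception is made for the AUC.
- **Primary endpoint (2.1).** The AUC of the combined symptom and medication score, "according to time from the start of treatment until the end of the patient follow-up". It is not divided by days observed.
- **Primary test (7.2).** An independent t-test on the "evolution (AUCs) of the two study groups over the whole treatment period". Secondary p-values are indicative only, so this is the one confirmatory test.
- **Primary cohort (7.2).** ITT: patients with at least one dose "in whom at least one efficacy or safety information has been collected after V0".
- **Sample size (7.2).** 50 per group "in order to achieve at least 40 evaluable patients per group taking into account a potential drop-out rate of 20" per cent. Section 4.1 and the scenario table count completed patients.
- **Discontinuation (6.4).** Under "Criteria for premature discontinuation of the study" the protocol lists "Voluntary discontinuation of treatment", as well as intolerance and use of a forbidden treatment.
- **Diaries (7.1, 6.2).** Cards are on paper and come back at the next visit. After V0 there are only V1 and V2.
- **Role of the SAP (7.2).** It is the reference document for statistical methods.

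The quality-of-life AUC in 2.2 ("total score of 3 questions of QoL included in the diary card on the Y-axis, and time on X axis") falls under the same missing-data rule, but it is a secondary endpoint.

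**The concern.** A cumulative total of a non-negative daily score cannot be left alone when days are missing. Leaving the gap unfilled scores every unobserved day as zero, the best possible value. Dropping the patient gives up the ITT comparison. The protocol does not say which applies. The count of evaluable and completed patients fits dropping leavers. The ITT definition, and an endpoint that runs to the end of each patient's own follow-up, fit keeping them. A patient with one adverse-event record and no returned diary is in the primary cohort with no AUC at all.

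At stake is the only confirmatory test. Depending on which arm loses which patients, the result could show a benefit that is not there or understate one that is. Data collection widens the gap: stopping treatment is listed as leaving the study, and diary days never filled in cannot be recovered later.

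**Working it through.** **1. The plan's own figures.** With difference 25, SD 30, two-sided alpha 0.05 and 90% power (7.2), the normal approximation is n = 2 × (1.960 + 1.282)² × 30² / 25² = 2 × 10.51 × 1.44 = 30.3, so 31 per group. The noncentral t gives 32, and it gives 15/23/32/43/55 across the five SDs, as printed. Enrolment: 40 / (1 − 0.20) = 50. The sample size is not in dispute.

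**2. The AUC is a total.** The daily score is at most 15 symptom points plus 5 or 6 medication points (2.1). Planning means of 80 and 55 cannot be daily averages.

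**3. Inputs for the checks.** From 7.2: means 80/80 (no effect) or 80/55, SD 30, 50 per arm. Assumed: how the 20% drop-out splits between arms, when patients leave, and how leaving relates to the score. Splits are written placebo/active. The simulations used gamma-distributed AUCs and a pooled two-sided t-test.

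**4. Partial totals.** Let p be the share of patients leaving and f the share of the full AUC accrued by then. If leaving is unrelated to outcome, the arm mean is μ × [1 − p(1 − f)].
- No effect: false difference = 80 × (1 − f) × (p active − p placebo). At 15%/25% and f = 0.5 this is 80 × 0.5 × 0.10 = 4.0.
- True difference 25, 20%/20%, f = 0.5: 25 × (1 − 0.20 × 0.5) = 22.5.

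| Setting | Estimated difference | Rejection |
|---|---|---|
| No effect, 20%/20%, same timing | 0 | 5% |
| No effect, 15%/25% | 2.7–4.0 | 6–10% |
| No effect, 10%/30% (upper illustration) | 5.3–8.1 | 12–22% |
| True 25, 20%/20% | 22.5–23.3 | 93–94% |

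The ranges run from a bell-shaped season peaking two months after V0 (lower bias) to a uniform share kept.

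**5. Absent AUCs (completers).** Where leaving is score-related, its log-odds rise by 1 per SD of the patient's own AUC (by 1 to 2 in the fifth row).

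| Setting | Estimated difference | Rejection |
|---|---|---|
| No effect, 10%/30%, unrelated to score | 0 | 5% |
| No effect, 20%/20%, same relation in both arms | 0 | 5% |
| No effect, 20%/20%, relation in active arm only | 5.8 | 14% |
| No effect, 15%/25%, related in both | 2.4 | 7% |
| No effect, 10%/30%, related in both (upper illustration) | 4.8–6.8 | 12–24% |
| True 25, 20%/20%, unrelated | 25.0 | 95% |
| True 25, 20%/20%, relation in placebo arm only | 19.1 | 84% |

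**6. How unusual the splits are.** If both arms truly lose 20%, a gap of at least 5 patients occurs in 25.9% of trials and of at least 10 in 1.7%. Such chance gaps go either way and do not by themselves raise the long-run error rate.

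**7. Candidate remedies.** These were checked with six monthly scores, 1,000 trials and 20 imputations. Monte Carlo error is about 0.7 percentage points at 5%.
- *Dividing by days observed*, no effect, 10%/30%: −6.9 points, 10% rejection. Patients who leave after the peak miss the quiet months, so their daily average is too high.
- *Multiple imputation, leaving driven by the last observed month*, no effect: 0.1 points (4.8%) at 10%/30%; −0.1 (5.8%) at 20%/20% with the relation in the active arm only.
- *Multiple imputation, leaving driven by the unseen next month*, no effect: 2.6 points against 4.3 for completers at 10%/30%; 3.0 against 5.1 at 20%/20% with the relation in the active arm only. Imputing active-arm leavers from the placebo-arm model lowers these only to 2.3 and 2.7.
- *True difference 25*, 30%/10%, last-month mechanism: imputation returned 26.0. The standard error of one estimate is about 30 × √(2/50) = 6, so that of the average is 6/√1000 = 0.19. The overshoot of about one point is real and unexplained.

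The repeated-measures model was not simulated.

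**The case against.** The strongest reply is that the protocol does not predict the harm. The placebo is identical and blinded (5.4), no side effects have been reported (1.1, 1.3), and rescue medication is open to both arms and counted in the score. If leaving is balanced and alike, both readings keep the error at 5%. The counts of completed and evaluable patients favour the absent-AUC reading, whose results are milder. All of this stands, and it limits the point to a conditional risk.

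Four stronger readings are tempting but unsupported:
- *The protocol leaves no way to correct the bias.* A repeated-measures model imputes nothing, and 7.2 makes the SAP the reference for methods.
- *Only two readings exist.* An AUC per observed day is a third. The seasonal score distorts it, but the rule does not forbid it.
- *A false-positive rate of 20% or more is to be expected.* That needs a split such as 10%/30%, or sharply different timing in the two arms, and the documents give no basis for either.
- *The three wordings of the AUC window (2.1, 6.2, 7.2) define different endpoints.* For a completer, diary entry and drug supply both end at V2, so they cover the same data. V2 itself may fall at six months or at the end of the peak, so the wording still needs tidying.

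Sections 6.4 and 7.1 are also silent on recovering open diary cards. They do not say that cards are lost.

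**Conclusion.** The point holds as a defect in a rule that the protocol itself fixes, and should be corrected. A ban on replacement or extrapolation, a cumulative AUC, an ITT cohort open to patients with almost no diary data and 20% drop-out do not fit together. The validity of the confirmatory test then rests on balanced leaving, which nothing in the protocol secures.

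On moderate assumptions the size is a few AUC points against a planned difference of 25, with a false-positive rate of up to about 10% (partial totals, 15%/25%) or about 14% (completers, score-related leaving in the active arm only). It is nil when leaving is balanced and alike. The direction cannot be told in advance. Confidence is high that the rule and the endpoint conflict; whether material bias would occur depends on drop-out patterns that the documents do not give.

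**What to change.** 1. **Primary AUC.** Replace the no-replacement rule with a stated method that uses all observed diary data in the ITT cohort over one defined window. Either fit a repeated-measures model to period means of the daily score, which imputes nothing, or multiply impute missing periods, apply the planned t-test and pool by Rubin's rules. Use neither raw partial totals nor simple division by days observed. Add a sensitivity analysis for leaving that depends on unseen scores, with a penalty for active-arm leavers clearly less favourable than the placebo-arm model, since that model removes little of the bias when there is no effect.
2. **Data collection.** State that diaries continue to V2 after study drug is stopped unless consent is withdrawn, and that open cards are recovered. Reconcile this with 6.4. Treatment decisions are unchanged.
3. **Window.** Use one wording in 2.1, 6.2 and 7.2.

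The quality-of-life AUC may follow the same rule in the SAP. Item 2 must be settled before diaries are issued; the analysis rule can be settled any time before unblinding.

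The cost is protocol and SAP wording, modest analysis work and some extra diary pages, with no extra patients. Bias is reduced, not eliminated, if leaving depends on scores that were never recorded.
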